### **7.6.1 Deaths**

See Core Safety SAP.

### **7.6.2 Serious Adverse Events**

See Core Safety SAP.

### **7.6.3 Adverse Events Leading to Discontinuation of Study Therapy**

See Core Safety SAP.

### **7.6.4 Adverse Events Leading to Dose Delay of Study Therapy**

See Core Safety SAP.

### **7.6.5 Adverse Events**

See Core Safety SAP.

### **7.6.6 Select Adverse Events**

See Core Safety SAP.

### **7.6.7 Immune Modulating Medication**

See Core Safety SAP.

### **7.6.8 Multiple Events**

See Core Safety SAP.

### **7.6.9 Clinical Laboratory Evaluations**

#### **7.6.9.1 Hematology**

See Core Safety SAP.

## 8 CONVENTIONS

The following conventions may be used for imputing partial dates for analyses requiring dates:

For missing and partial adverse event onset dates, imputation will be performed using the Adverse Event Domain Requirements Specification. Missing and partial Non-Study Medication Domain dates will be imputed using the derivation algorithm described in 4.3.3 of BMS Non-Study Medication Domain Requirements Specification.

For death dates, the following conventions will be used for imputing partial dates:

- If only the day of the month is missing, the 1st of the month will be used to replace the missing day. The imputed date will be compared to the last known date alive day and the maximum will be considered as the death date.
- If the month or the year is missing, the death date will be imputed as the last known date alive day
- If the date is completely missing but the reason for death is present the death date will be imputed as the last known date alive day

For date of progression, the following conventions will be used for imputing partial dates:

- If only the day of the month is missing, the 1st of the month will be used to replace the missing day\*.
- If the day and month are missing or a date is completely missing, it will be considered as missing.

\*In cases where the date of death is present and complete, the imputed progression date will be compared to the date of death. The minimum of the imputed progression date and date of death will be considered as the date of progression.

For other partial/missing dates, the following conventions may be used:

- If only the day of the month is missing, the 15th of the month will be used to replace the missing day.
- If both the day and the month are missing, “July 1” will be used to replace the missing information.
- If a date is completely missing, it will be considered as missing.

The following conversion factors will be used to convert days to months or years: 1 month = 30.4375 days and 1 year = 365.25 days.

Duration (e.g. time from first diagnosis to first dosing date, duration of response, and time to response) will be calculated as follows:

$$\text{Duration} = (\text{Last date} - \text{first date} + 1)$$

All statistical analyses will be carried out using SAS (Statistical Analysis System software, SAS Institute, North Carolina, USA) unless otherwise noted.

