### **4.2 Secondary**

The secondary objective (to assess the safety and tolerability of nivolumab monotherapy or nivolumab combined with ipilimumab in subjects with advanced or metastatic tumors) will be primarily assessed by the rate of treatment-related AEs leading to drug discontinuations during the first 12 weeks of treatment. In addition, safety and tolerability will be analyzed through the incidence of adverse events, serious adverse events, and specific laboratory abnormalities (worst grade) in each cohort. Toxicities will be graded using the National Cancer Institute (NCI) Common Terminology Criteria for Adverse Events (CTCAE) version 4.0.

ORR will be further characterized by the duration of response (DOR) and the magnitude of reduction in tumor volume. DOR will be computed for subjects with a BOR of PR or CR and is defined as the time from first confirmed response (CR or PR) to the date of the first documented

tumor progression as determined using RECIST 1.1 criteria or death due to any cause, whichever occurs first. For subjects who neither progress nor die, the DOR will be censored on the date of their last evaluable tumor assessment. Subjects who start subsequent therapy without a prior reported progression will be censored at the last evaluable tumor assessments prior to initiation of the subsequent anticancer therapy. The magnitude of reduction in tumor volume is defined as the percent decrease in tumor volume from baseline to nadir, observed up until the time of the first documented tumor progression or death.

Progression free survival (PFS) is defined as the time from first dosing date to the date of the first documented progression, as determined by the investigator or BICR for selected tumor type (per RECIST 1.1), or death due to any cause, whichever occurs first. Subjects who die without a reported progression or start of any subsequent anti-cancer therapy will be considered to have progressed on the date of their death. Subjects who did not progress or die will be considered as not progressed and will be censored on the date of their last evaluable assessment or last evaluable assessment prior to crossover. Subjects who did not have any on study assessments and did not die will be censored on the first dosing date. Subjects who started any subsequent anti-cancer therapy without a prior reported progression will be censored at the last evaluable assessment prior to initiation of the subsequent anti-cancer therapy.

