**Table 4.2: Censoring scheme used in primary analysis of PFS**

Situation	Date of Progression or Censoring	Outcome
No baseline tumor assessments and no death	First Dosing date	Not Progressed
No on study tumor assessments and no death	First Dosing date	Not Progressed
Progression documented between scheduled visits	Date of the first documented tumor progression per RECIST 1.1	Progressed
Clinical progression without evidence of progression per RECIST 1.1 or No progression	Date of last tumor assessment with no documented progression or last evaluable assessment prior to crossover (for crossover subject without PD)	Not Progressed
New anticancer treatment started without a prior reported progression	Date of last tumor assessment prior or on the date of initiation of the subsequent anti-cancer therapy	Not Progressed
Death without progression per RECIST 1.1	Date of death	Progressed

OS is defined as the time between the first dosing date and the date of death due to any cause. A subject who has not died will be censored at the last known alive date. OS will be followed continuously while subjects are on the study drug and every 3 months via in-person or phone contact after subjects discontinue the study drug.

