## 8 CONVENTIONS

The following conventions may be used for imputing partial dates for analyses requiring dates:

For missing and partial adverse event onset dates, imputation will be performed using the Adverse Event Domain Requirements Specification. Missing and partial Non-Study Medication Domain dates will be imputed using the derivation algorithm described in 4.3.3 of BMS Non-Study Medication Domain Requirements Specification.

For death dates, the following conventions will be used for imputing partial dates:

- If only the day of the month is missing, the 1st of the month will be used to replace the missing day. The imputed date will be compared to the last known date alive day and the maximum will be considered as the death date.
- If the month of the year is missing, the death date will be imputed as the last known date alive day.
- If the date is completely missing but the reason for death is present, the death date will be imputed as the last known date alive day.

For date of progression, the following conventions will be used for imputing partial dates:

- If only the day of the month is missing, the 1st of the month will be used to replace the missing day\*.
- If the day and month are missing or a date is completely missing, it will be considered as missing.

\*In cases where the date of death is present and complete, the imputed progression date will be compared to the date of death. The minimum of the imputed progression date and date of death will be considered as the date of progression.

For other partial/missing dates, the following conventions may be used:

- If only the day of the month is missing, the 15th of the month will be used to replace the missing day.
- If both the day and the month are missing, “July 1” will be used to replace the missing information.
- If a date is completely missing, it will be considered as missing.

The following conversion factors will be used to convert days to months or years: 1 month = 30.4375 days and 1 year = 365.25 days.

Duration (e.g. time from first diagnosis to first dosing date, duration of response, and time to response) will be calculated as follows:

$$\text{Duration} = (\text{Last date} - \text{first date} + 1)$$

All statistical analyses will be carried out using SAS (Statistical Analysis System software, SAS Institute, North Caroline, USA) unless otherwise noted.

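### A death with a recorded year but no month is set to the last known alive date, which can fall in a year before the recorded year of death

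*SAP*

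**What the plan says.** Section 8 (Conventions) of SAP v2.0 has three rules for incomplete death dates.

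- **Day missing:** "If only the day of the month is missing, the 1st of the month will be used to replace the missing day". A safeguard follows: "The imputed date will be compared to the last known date alive day and the maximum will be considered as the death date".
- **Month or year missing:** "If the month or the year is missing, the death date will be imputed as the last known date alive day".
- **Whole date missing, reason for death present:** the last known alive date again ("If the date is completely missing but the reason for death is present the death date will be imputed as the last known date alive").

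Section 8 of the SCLC expansion SAP repeats these rules, with one word changed in the second: "If the month of the year is missing, the death date will be imputed as the last known date alive day". Read literally, that wording covers a missing month but no longer names a missing year.

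For dates other than AE onset, non-study medication, death and progression, both SAPs keep a known year: "If both the day and the month are missing, “July 1” will be used to replace the missing information".

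The death date feeds the time-to-event endpoints directly. For OS: "OS is defined as the time between the first dosing date and the date of death due to any cause". For PFS, Section 4.2 puts the event on the death date when a subject dies with neither a reported progression nor later anti-cancer treatment. Section 4.2 also counts death from any cause as a DOR event.

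**The concern.** The day-missing rule uses everything that is known. Death cannot precede the recorded month or the last known alive date, so the later of the two is taken. The month-missing rule drops that logic. A recorded year is ignored, and the subject is handled as if nothing about the date were known.

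Where the last known alive date and the recorded death are in the same calendar year, the result is early but possible. Where the last known alive date is in an earlier year, the analysis dataset holds a death date that the case record rules out.

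The error runs one way. It shortens OS, and it shortens PFS or DOR when death is the event. It could move a death to the other side of a reported landmark such as 6 or 12 months. It is also a traceability problem, because the derived date contradicts its source.

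**Working it through.** The plan states no figure to reproduce, so the check applies the rule to dates and then asks how often the problem can arise.

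**1. Rules side by side when part of the date is known**

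| Known part | Rule in Section 8 | Known part respected? |
|---|---|---|
| Death: month and year | later of the 1st of that month and last known alive date | yes |
| Death: year only | last known alive date | not checked |
| Death: nothing | last known alive date | not applicable |
| Other dates: year only | 1 July of that year | yes |

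**2. Worked dates (invented for illustration)**

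First dose is 1 June 2015 and death is recorded as 2016 with no month. OS in months = (death − first dose + 1) / 30.4375, using the Section 8 duration formula and conversion factor.

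- *Last known alive 20 November 2015, plan's rule.* Death is set to 20 November 2015: (172 + 1) / 30.4375 = 5.68 months. The imputed year, 2015, contradicts the record.
- *Same subject, later of 1 January 2016 and last known alive date.* Death is set to 1 January 2016: (214 + 1) / 30.4375 = 7.06 months, which is 42 days later.
- *Last known alive 10 February 2016.* Both rules give 10 February 2016. There is no conflict.

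Had the record said January 2016 with only the day missing, the plan's own day-missing rule would have given 1 January 2016 for the first subject. Knowing slightly less moves the imputed death 42 days earlier and into the wrong year.

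**3. How often, and by how much**

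Both SAPs plan OS contact every 3 months after study drug stops, about 91 days. Assumptions: death is uniform over the calendar year, and the gap from last known alive date to death is uniform on 0 to G days, independent of the time of year.

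- Share with last known alive date in the previous year = (G/2) / 365.25
- Mean shortfall among these, measured to 1 January = (G²/3) / G = G/3
- Maximum shortfall = G
- Mean bias over all such deaths is −G/2 under the plan's rule, and −G/2 + share × G/3 under the bounded rule

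| G (days) | Share affected | Mean shortfall (days) | Maximum (days) | Mean bias, plan (days) | Mean bias, bounded (days) |
|---|---|---|---|---|---|
| 30 | 15/365.25 = 4.1% | 10 | 30 | −15.0 | −14.6 |
| 91 | 45.5/365.25 = 12.5% | 30.3 | 91 | −45.5 | −41.7 |
| 182 | 91/365.25 = 24.9% | 60.7 | 182 | −91.0 | −75.9 |

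A simulation of 2,000,000 deaths per row agrees: shares of 4.1%, 12.4% and 24.9%, and mean shortfalls of 10.0, 30.3 and 60.8 days.

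**The case against.** The best case for leaving the rule alone is that it hardly matters. An impossible date needs a missing month, a recorded year, and a last known alive date in an earlier calendar year, all together. With contact as planned, about 88% of month-missing deaths are untouched. OS, PFS and DOR are secondary Kaplan-Meier summaries with no between-arm test specified, and the definition of ORR uses no death date. Early imputation is also conservative for survival. All of this stands as to size. It does not justify a derived date that contradicts the record. Nor is a conservative default the plan's consistent principle, since its day-missing rule overrides the last known alive date whenever the record shows it to be too early.

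Three stronger readings are tempting, and the documents do not support them.

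- *Deaths long after treatment would be counted as close to the last dose.* Both SAPs refer death summaries to the Core Safety SAP, which is not shown. The 30/100-day windows in Section 6.1.2 are defined for adverse events and for laboratory, oximetry and vital-sign evaluations. AE onset dates have their own imputation specification. Nothing visible feeds the imputed death date into a count of time since last dose.
- *Deaths with a missing month are mostly learned of late, in subjects out of contact.* The SAPs say nothing on this.
- *The error commonly exceeds a year.* That is arithmetically possible: last known alive on 15 June 2015 with death recorded as 2017 gives 566 days to 1 January 2017. It needs about 18 months without the planned 3-monthly contacts, so it is no guide to usual size.

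**Conclusion.** The point holds as a minor defect of internal consistency. As written, both SAPs can place a death before the earliest date the record allows, and no visible text corrects this.

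Under a uniform 0 to 91 day gap, about 12% of deaths with a known year and missing month are affected, by about 30 days on average and at most 91. The share runs from about 4% to 25% for maximum gaps of 30 to 182 days. These percentages refer only to month-missing deaths. The documents do not give their number, which is probably small. The logic of the rule is certain, whereas the practical effect rests on the assumed gap.

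It would be wrong to infer that bounding the date repairs OS. The bounded rule also takes the earliest admissible date, and at a 91-day gap the mean bias over month-missing deaths moves only from about −45 to about −42 days. The gain is agreement with the record, not a material change in the survival estimates.

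**What to change.** In Section 8 of both SAPs, replace the second death-date bullet with:

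> If the month is missing and the year is known, the death date is the later of 1 January of the recorded year and the last known date alive; if the year is missing, the last known date alive is used.

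This extends the principle of the day-missing rule. It changes nothing when the last known alive date is in the recorded year of death, and it removes the difference in wording between the two SAPs. The cost is one sentence in each SAP and one line of derivation code, with no new data.

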## 9 CONTENT OF REPORTS

All analyses described in this SAP will be included in the Clinical Study Report(s) except where otherwise noted. Refer to the Data Presentation Plan for mock-ups of all tables and listings.

- [REDACTED]
- [REDACTED]
- [REDACTED]
- [REDACTED]
- [REDACTED]

**STATISTICAL ANALYSIS PLAN  
FOR CLINICAL STUDY REPORT - SCLC EXPANSION COHORT**

**A PHASE 1/2, OPEN-LABEL STUDY OF NIVOLUMAB MONOTHERAPY OR  
NIVOLUMAB COMBINED WITH IPILIMUMAB IN SUBJECTS WITH ADVANCED OR  
METASTATIC SMALL CELL LUNG CANCER (SCLC)**

## 2 STUDY DESCRIPTION

### 2.1 Study Design

This is a Phase 1/2, open-label study of nivolumab monotherapy (Arm N), or nivolumab combined with ipilimumab (Arm N-I) in adult ( $\geq 18$  years) subjects with advanced or metastatic SCLC. Subjects will be assigned to one of the following treatment arms:

- Arm N:** Nivolumab monotherapy (3 mg/kg) Q2W
- Arm N-I Dose Level 1:** Nivolumab (1 mg/kg) + Ipilimumab (1 mg/kg) Q3W for 4 doses, then Nivolumab (3 mg/kg) Q2W
- Arm N-I Dose Level 2:** Nivolumab (1 mg/kg) + Ipilimumab (3 mg/kg) Q3W for 4 doses, then Nivolumab (3 mg/kg) Q2W
- Arm N-I Dose Level 2b:** Nivolumab (3 mg/kg) + Ipilimumab (1 mg/kg) Q3W for 4 doses, then Nivolumab (3 mg/kg) Q2W

#### **SCLC Pre-Expansion Cohort:**

**Dose-Escalation Safety Evaluation Phase for Combination Arm:** Although the regimen used in the phase 3 melanoma study, nivolumab 1 mg/kg + ipilimumab 3 mg/kg, was expected to also be tolerable in the tumor studied here, an initial dose-escalating safety evaluation for the combination arms was conducted for the SCLC pre-expansion cohort.

Enrollment to Stage 1 for Arm N occurred in parallel to the safety evaluation for Arm N-I.

**Two Stage Design:** SCLC Arms N and N-I followed a two-stage design to test whether nivolumab monotherapy or nivolumab combined with ipilimumab yield an objective response rate (ORR) that is of clinical interest. Only treatment arms which met an ORR threshold proceeded from Stage 1 to Stage 2 (described in protocol Section 3.1.3). Enrollment to Stage 2 in a given treatment arm continued even if the other treatment arm was still in Stage 1.

For Stage 2, additional subjects were assigned into Arm N, and Arm N-I up to a total of 100 subjects (including those assigned in Stage 1) in each treatment arm. Assessment of Dose Level 2b in Stage 2 (nivolumab 3 mg/kg + ipilimumab 1 mg/kg, n= up to 70 subjects) were initiated when nivolumab monotherapy or nivolumab 1 mg/kg + ipilimumab 3 mg/kg proceeded to Stage 2.

**Crossover for subjects in Arm N:** Subjects in SCLC pre-expansion cohort Arm N were permitted to crossover to Arm N-I if all of the following criteria were met:

- The Safety Evaluation Phase for the N-I regimen had been completed and at least 6 subjects had been exposed to the dose level used for Stage 1 of the N-I regimen. In case Dose Level 2b had been activated and completed the safety assessments, subjects for crossover were assigned to Dose Level 2b.
- Subject had further disease progression (investigator-assessed RECIST 1.1-defined progression confirmed at least 4 weeks after the initial tumor assessment showing progression) in the absence of clinical deterioration. For subjects with clear evidence of new or progression brain metastases a confirmation was not required. These subjects were permitted to proceed with brain radiation therapy and after having completed the radiation therapy a crossover to Arm N-I was considered.
- Subjects with rapidly progressing tumors under nivolumab monotherapy were permitted to undergo radiation treatment first before initiation of the crossover after discussion between the sponsor and investigator.
- Subject did not experience nivolumab related adverse events leading to permanent discontinuation.
- Subject did not continue to derive any clinical benefit from nivolumab single agent therapy as assessed by the investigator which would allow continuation of nivolumab monotherapy.
- The individual case was to be discussed with the medical monitor prior to crossover.

Subjects who crossed over to Arm N-I started treatment at Day 1 Week 1 as described for subjects originally assigned to Arm N-I. Subjects who crossed over and subsequently had an objective response in Arm N-I were not considered in the decision making for Arm N-I proceeding to Stage 2.

### **SCLC Expansion:**

SCLC pre-expansion cohort Arm N and Arm N-I met the pre-specified safety and efficacy criteria and proceeded to Stage 2. Based on an interim data review, disease control rates (SD + PR + CR) of 36% and 57% for Arms N and N-I, respectively, were estimated.

In order to further investigate nivolumab and nivolumab combined with ipilimumab activity in specific SCLC subpopulations, the SCLC expansion cohorts will enroll additional subjects based on response to prior treatment and the number of previous therapies. Up to 250 second or third line subjects will be randomized in a 3:2 ratio to one of 2 expansion groups: Arm A (75 second line

subjects and 75 third line subjects treated with nivolumab 3 mg/kg every 2 weeks (Q2W) or Arm B (50 second line subjects and 50 third line subjects treated with nivolumab 1 mg/kg + ipilimumab 3 mg/kg every 3 weeks (Q3W) for 4 cycles followed by nivolumab 3 mg/kg Q2W) and will be stratified for number of prior treatment lines (1 vs 2 prior chemotherapy regimens). Each arm will be limited to 50% third line subjects to allow a meaningful subgroup evaluation for subjects with second-line versus third-line disease. The crossover from Arm N to Arm N-I dose level 2 is not allowed for the SCLC expansion cohort.

Although crossover was not to be permitted for the SCLC expansion cohort, the interim results for the SCLC cohorts showed that two subjects in the SCLC expansion cohort crossed over; therefore, the handling of crossover subjects is described below for consistency.

## 2.2 Treatment Assignment

The subject number will be assigned through an interactive voice response system (IVRS) once the subject has signed the informed consent form and is registered. Every subject that signs the informed consent form must be assigned a subject number in IVRS. Specific instructions for using IVRS will be provided to the investigational site in a separate document.

The investigator or designee will register the subject for enrollment by following the enrollment procedures established by BMS. The following information is required for enrollment:

- Date that informed consent was obtained
- Date of birth
- Gender at birth

Once enrolled in IVRS, enrolled subjects that have met all eligibility criteria will be ready for treatment assignment and drug vial assignment through the IVRS. The following information is required for drug vial assignment and randomization:

- Subject number
- Date of birth
- Tumor Type
- Date tumor tissue sample was shipped to central lab

Subjects to be enrolled in the SCLC expansion cohort will be randomized in a 3:2 ratio to one of 2 expansion groups: nivolumab monotherapy arm (150 subjects, nivolumab 3 mg/kg every 2 weeks (Q2W) or N-I dose level 2 arm (100 subjects, nivolumab 1 mg/kg + ipilimumab 3 mg/kg every 3 weeks (Q3W) for 4 cycles followed by nivolumab 3 mg/kg Q2W) and will be stratified for number of prior treatment lines (1 vs 2 or more prior chemotherapy regimens).

